If the research includes survey or interview procedures, the questionnaire, interview questions or assessment scales should be included in the application (use attachment button below).

The data collection instrument(s) can be submitted with your application in draft form with the understanding that the final copy will be submitted to the IRB for approval prior to use (submit final version to the IRB for review as a modification request if initial IRB approval was issued while the data collection instrument was in draft form).

Note: The IRB approval process does not include a statistical review. Investigators are strongly encouraged to develop data management and analysis plans in consult with a statistician.

Demographics (age, sex, race, past medical history), chief complaint, sequential organ failure assessment score, vasopressor dosing, lactate, requirement for mechanical ventilation, requirement for renal replacement therapy, serum creatinine values, blood pressure. Monitoring of side effects including: venous thromboembolism, arrhythmia, extremity hypoperfusion, delirium, new ischemic event, new infection), and any others deemed pertinent per the institution that may be related to angiotensin II. Patient outcomes including: in-hospital mortality, ICU and hospital length of stay, acute kidney injury and needed for renal replacement therapy. Lab values for renin and functional biomarkers of renal function at the time points described (cystatin C, NGAL, angiotensin II, angiotensin 1-7).

Attachments

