Benefit vs. Risk: Describe potential benefits to the subject(s); include potential benefits to society and/or general knowledge to be gained. Describe why the risks to subjects are reasonable in relation to the anticipated benefit(s) to subjects and in relation to the importance of the knowledge that may reasonably be expected to result. If you are using vulnerable subjects (e.g., impaired consent capacity, pregnant women, etc...), justify their inclusion by describing the potential benefits of the research in comparison to the subjects' vulnerability and the risks to them. For information about inclusion of certain vulnerable populations, see the IRB/ORI Standard Operating Procedure for Protection of Vulnerable Subjects [C3.0100] [\[PDF\]](#).

Control group- There is no direct benefit to subjects in the control arm.

Angiotensin II- We do not know if subjects in this group will benefit directly, but hypothesized benefits include less kidney failure (which we are measuring with biomarkers) and fewer vasopressors required to maintain their blood pressure. Risks are outlined in the informed consent document and notably include venous thromboembolism. Given the mortality rate observed with septic shock, the FDA's decision to approve this medication suggest there may be patients that benefit from this drug despite the risks. We have attempted to use the literature to guide our protocol to reflect those patients most likely to benefit. For example, we have focused on acute kidney injury, in which a subgroup analysis from the phase III approval trial suggested improved survival and less dependence on dialysis by day 7 in the subgroup of patients receiving angiotensin II. We have also carefully selected the norepinephrine dose equivalents to reflect those that are severe enough to warrant addition of a second vasopressor, but not high enough that the patient is unlikely to respond to any additional vasopressor (again suggested by a subgroup analysis of the pivotal phase III trial).

Available Alternative Treatment(s): Describe alternative treatments and procedures that might be advantageous to the subjects, should they choose not to participate in the study. This should include a discussion of the current standard of care treatment(s).

The only other treatment choice for septic shock at the point that the patient would meet inclusion criteria includes continuing to increase the dose of the vasopressor agent.

[Back to Top](#)

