Following enrollment of the 10 patients in the control arm and 10 patients in the angiotensin II arm (i.e. half of the 20 patients that will ultimately receive the drug), we will evaluate the risk of venous thromboembolism and any additional reported thrombotic reports from the 10 patients that have received angiotensin II. Groups will be compared using a Fisher's exact test given the small sample size. Given the concern for safety, if the p-value is 0.15 or less with increased thrombotic events in the angiotensin II group, the open-label study will be stopped. For example, assuming a baseline rate of thrombotic events of 1/10 (10%) in the control arm, if 5/10 patients in the angiotensin II group (50%) experienced a thrombotic event, a Fisher exact test yields p=0.141 and the open-label use of angiotensin II would be stopped due to concern for safety. If thrombotic event differences do not meet this threshold, we will continue with the enrollment of an additional 10 patients to meet the 20 patient enrollment set.

[Back to Top](#)

Subject Complaints: Describe procedures (other than information provided in consent document) for handling subject complaints or requests for information about the research. The procedures should offer a safe, confidential, and reliable channel for current, prospective, or past research subjects (or their designated representative) permitting them to discuss problems, concerns and questions, or obtain information.

Subject complaints will be directed to the primary investigator, who will contact the subjects to discuss their concerns, including potential withdraw from the study or use of their information. If a subject has any concerns or questions about his/her rights as a volunteer in this research, they will be advised to contact staff in the Office of Research Integrity (ORI).

Does your research involve **Non-English Speaking Subjects or Subjects from a Foreign Culture?**

Yes No

—Non-English Speaking Subjects or Subjects from a Foreign Culture—

Describe how information about the study will be communicated to potential subjects appropriate for their culture, and if necessary, how new information about the research may be relayed to subjects during the study.

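### In the text supplied, the only study-level stopping rule counts thrombotic events alone and otherwise commits to continuing, so deaths have no role at the interim look and the handling of patients who die without a clot is undefined

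*Combined protocol and SAP*

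**What the plan says.** The rule stands under Data and Safety Monitoring and is repeated under Interim Analysis in the SAP part.

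- Timing: "Following enrollment of the 10 patients in the control arm and 10 patients in the angiotensin II arm".
- What is counted: "we will evaluate the risk of venous thromboembolism and any additional reported thrombotic reports from the 10 patients that have received angiotensin II".
- Test: "Groups will be compared using a Fisher's exact test given the small sample size".
- Stop: "if the p-value is 0.15 or less with increased thrombotic events in the angiotensin II group, the open-label study will be stopped".
- Otherwise: "If thrombotic event differences do not meet this threshold, we will continue with the enrollment of an additional 10 patients". No further condition is attached.

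Data Collection lists other safety information. The side effects are "venous thromboembolism, arrhythmia, extremity hypoperfusion, delirium, new ischemic event, new infection", and the outcomes begin "Patient outcomes including: in-hospital mortality, ICU and hospital length of stay". No text links any of these to a pause, review or stop, except where an event is reported as thrombotic. Safety Precautions relies on the routine intensive-care monitoring of each patient and gives no rule for the study as a whole. No section says how a patient who dies without a thrombotic event enters the interim table.

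**The concern.** The stopping rule has a single input and a firm commitment to go on when that input is quiet. The population is one in which death is common enough that Benefit vs. Risk argues from it ("Given the mortality rate observed with septic shock"), and that section also cites a suggested survival gain in a subgroup. Survival is thus part of the case for exposing patients, but it is absent from the decision whether to expose 10 more. Ischemia or hypoperfusion that is not reported as thrombotic is absent too, although Potential Risks names peripheral ischemia as a risk of the drug.

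A second gap follows from the same rule. A patient who dies early may have had no chance to show a thrombotic event. Whether that patient counts as event-free or leaves the denominator can decide a table of this size, and the plan is silent.

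**Working it through.** **Inputs from the documents.** 10 v 10 patients, Fisher's exact test, stop at p ≤ 0.15 with more events on angiotensin II, and a worked example of 5/10 v 1/10 with p=0.141. The documents give no mortality figure, so every death rate below is an assumption.

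**1. The plan's own figure.** With 6 events in 20 patients, the number of possible tables is C(20,6) = 38,760. The upper tail is C(10,5)·C(10,1) + C(10,6)·C(10,0) = 2,520 + 210 = 2,730. By symmetry, two-sided p = 2 × 2,730 / 38,760 = 0.1409, which matches. The one-sided value, 0.0704, does not. The rule is therefore read as two-sided with a direction added.

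**2. Deaths against the rule.** Take deaths of 9/10 on drug and 3/10 on control, with one thrombotic event in each arm.

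- Deaths: C(20,12) = 125,970. The upper tail is C(10,9)·C(10,3) + C(10,10)·C(10,2) = 1,200 + 45 = 1,245. Two-sided p = 2 × 1,245 / 125,970 = 0.020.
- Thrombosis, 1/10 v 1/10: p = 1.0, so the rule says continue.

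Deaths of 8/10 v 3/10 (p=0.070) give the same decision. So do 10/10 v 0/10 deaths with no thrombotic events, because deaths never enter the calculation.

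**3. One death without a thrombotic event, in the plan's example.** Suppose one of the five treated patients dies before the event is seen.

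| Handling of that patient | Table | Two-sided p | Decision |
|---|---|---|---|
| Event is seen (plan's example) | 5/10 v 1/10 | 0.141 | stop |
| Kept as event-free | 4/10 v 1/10 | 2 × (2,100 + 252) / 15,504 = 0.303 | continue |
| Dropped from the denominator | 4/9 v 1/10 | (1,260 + 126 + 252) / 11,628 = 0.141 | stop |

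The decision turns on a convention that the plan does not state.

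**4. The same test applied to deaths.** Listing all 10 v 10 tables gives the fewest treated-arm deaths that reach p ≤ 0.15:

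| Control deaths | 0 | 1 | 2 | 3 | 4 | 5 | 6 | 7 or more |
|---|---|---|---|---|---|---|---|---|
| Treated deaths needed | 4 | 5 | 7 | 8 | 9 | 9 | 10 | never |

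Write b(c) for the boundary at c control deaths. Then P(hold) = Σ over c of Bin(c; 10, control rate) × P(treated deaths ≥ b(c)).

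| Assumed true mortality, drug v control | P(hold) |
|---|---|
| 20% v 20% | 2.2% |
| 30% v 30% | 3.1% |
| 40% v 40% | 2.9% |
| 50% v 50% | 2.6% |
| 60% v 60% | 2.9% |
| 60% v 40% | 14% |
| 60% v 30% | 28% |
| 80% v 30% | 65% |

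**The case against.** Thrombosis is a reasoned choice. Background explains at length that it is the labelled warning (13% v 5%), so the rule watches the known harm of an approved drug. That is a good reason to count thrombosis. It is no reason to commit to continuing whatever else has happened.

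Three stronger readings are tempting, and the documents do not support them.

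- *Early deaths make the drug look safer.* A reader might infer this from the 4/10 v 1/10 result. It holds only if the dead patient stays in the denominator as event-free; with that patient dropped, 4/9 v 1/10 still stops. A fatal thrombotic event would count as an event. The plan's example uses 10 per arm but involves no deaths. What is established is an undefined convention, and not a bias of known direction.
- *Ischemic events never enter the look.* The rule includes other reported thrombotic events, so an ischemic event reported as thrombotic would plausibly count. Only death and non-thrombotic ischemia or hypoperfusion are clearly outside.
- *An excess of deaths cannot stop the study.* The investigator or the IRB could act outside the written rule. A proposal is listed as an attachment but is not in the file, and the monitoring-board checkbox cannot be read. The finding is limited to the text supplied.

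Two limits on the remedy stand. Under Study Design the 10 controls are enrolled first and there is no randomisation, so a death imbalance may reflect case mix. It can prompt review but cannot show harm. And at 10 v 10 the death comparison is insensitive to moderate differences. The look also follows enrolment directly, so in-hospital outcomes of the most recent treated patients may be incomplete when those of the controls are known.

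**Conclusion.** The point holds for the text supplied. The one study-level rule ignores in-hospital death and non-thrombotic ischemia or hypoperfusion, and it commits to 20 treated patients whenever the thrombosis threshold is missed. Deaths of 9/10 v 3/10 (p=0.020) with equal thrombosis counts would send 10 more patients to the drug. This is a consequence of the rule as stated, beyond a missing detail.

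Separately, the treatment of patients who die without a thrombotic event is undefined, and one such patient can move the plan's own example between stop and continue. The conclusion rests on the two-sided reading that reproduces the plan's p-value. The death counts in the illustration are assumed. The point makes no claim that the drug raises mortality, or that deaths bias the rule in one direction.

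**What to change.** In both Data and Safety Monitoring and Interim Analysis:

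1. At the same 10 v 10 look, also compare in-hospital deaths by arm with the two-sided Fisher test at p ≤ 0.15, harmful direction only.
2. Replace the unconditional commitment with: enrolment continues only if neither the thrombotic nor the death threshold is met. If the death threshold is met, enrolment is held for IRB review. This is a hold and not an automatic stop, because of the sequential, non-randomised arms.
3. State that all treated patients stay in the thrombosis denominator.
4. Beside the thrombosis counts, tabulate by arm the deaths without a thrombotic event and the non-thrombotic ischemic or hypoperfusion events. Item 3 can lower the apparent thrombosis count, and this table makes that visible. These events are tabulated only and add no further test.

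The change takes a few sentences and uses data already collected. The price is a false hold from the death comparison in 2.2% to 3.1% of studies at equal true mortality of 20% to 60%. The gain is modest for moderate differences (14% at 60% v 40%, 28% at 60% v 30%) and larger for extreme ones (65% at 80% v 30%). All of these rates are assumed.

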The proposed protocol for this study was derived from a number of secondary analyses of the phase III trial, informing us which patients may be most likely to benefit from receiving the drug in septic shock. A secondary analysis of patients with acute kidney injury suggested improved survival through day 28 and increased liberation and therefore avoidance of dialysis through day 7 (5).

References:

- 1.) Giapreza (angiotensin II) [package insert]. San Diego, CA: La Jolla Pharmaceutical Company. 2018.

Objectives: List your research objectives. You may reference grant application/sponsor's relevant protocol pages and attach as an appendix in the E-IRB "Additional Information" section, however, a summary paragraph must be provided in the text box below.

- 1.) To determine if prescription of angiotensin II is associated with faster declines in plasma renin compared to a control group.
- 2.) To determine if prescription of angiotensin II is associated with improvement of functional renal biomarkers compared to a control group.

Study Design: Describe the study design (e.g., single/double blind, parallel, crossover, etc.). Indicate whether or not the subjects will receive placebo medication at some point in the research procedures. Also, indicate whether or not the subjects will be randomized in this study. You may reference sponsor's protocol pages and attach as an appendix in the E-IRB "Additional Information" section, however, a summary paragraph must be provided in the text box below. (Including the study design table from a sponsor's protocol is helpful to IRB members.)

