Once subjects are identified per the above process, an assessment will be made as described in form T by the study team member of whether the patient can provide informed consent. If ineligible, a legally authorized representative will be approached regarding the study. Informed consent will be sought once the patient meets the eligibility criteria as defined in the study protocol. If the legally authorized representative is not physically in the hospital due to visiting restrictions due to COVID-19, an electronic consent process will be sought as follows. The patient's LAR will be contacted via telephone and approached about the study in the same way that the LAR would be if they were physically present. If the LAR is interested in pursuing further, a member of the study team will send the LAR a RedCap link (<https://redcap.uky.edu/redcap/surveys/?s=7LWKY4JETE>) that has been designed for e-consent in this study. A member of the study team will walk the LAR through the e-consent document, which mirrors the written informed consent document exactly, and answer any questions along the way. If the LAR consents, they will sign the document using the e-sign feature in RedCap. A member of the study team will email the LAR back with a copy of the signed e-consent form.

[Back to Top](#)

Research Procedures: Describe the research procedures that will be followed. Identify all procedures that will be carried out with each group of subjects. Differentiate between procedures that involve standard/routine clinical care and those that will be performed specifically for this research project.

Control group (n=10): Standard of care will be followed for all aspects of care. The only procedure specifically involving research will be blood collection once the patient meets inclusion criteria (time T), 24 hours later (time T + 24 hours), and when the patient no longer requires vasopressor agents to support their blood pressure (defined as off of vasopressors for at least 4 hours). If the patient ceases vasopressor agents within 12 hours of the second blood draw, the third and final blood draw will not be collected.

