Intervention group (n=20): Standard of care will be followed for the management of septic shock. At which point the patient meets the inclusion criteria of the study, the patient's treating physician will be approached about the opportunity to offer angiotensin II to the patient. If the treatment team wishes to pursue, the patient or their LAR will be approached for written informed consent. Angiotensin II will be dosed per the protocol, and the patient will receive blood draw at the time they meet inclusion criteria (time T), 3 hours later (T+3), and 24 hours from angiotensin II initiation (T+24 hours), and when the patient no longer requires vasopressor agents to support their blood pressure (defined as off of vasopressors for at least 4 hours). If the patient ceases vasopressor agents within 12 hours of the third blood draw, the fourth and final blood draw will not be collected. All other aspects of the patient's care will be per the standard of care in the medical intensive care unit. Blood samples will be centrifuged, plasma extracted, and stored at -80 C. Commercial ELISAs will be used for analysis of renin and renal biomarkers (cystatin C, NGAL, renin, angiotensin II, angiotensin 1-7). COVID specification. Testing positive is a known exclusion criteria for the study. If a patient has results when evaluated for the study, this will be straightforward. However, if the test is pending while the patient is eligible for study entry, this will not make the patient ineligible for the study. If, in the opinion of the attending physician, COVID-19 is highly likely the patient will not be approached for informed consent. Otherwise, if COVID-19 test is pending, the patient or LAR will be approached for informed consent. If the test results as negative, study procedures will be performed as planned. If the test returns positive, the patient will be informed and dropped from the study. We will use their baseline information collected up to that point, but they will no longer receive blood draws or study medication (angiotensin II) once confirmed COVID positive. A case series of angiotensin II has been published in COVID 19

patients, and given the acuity of the disease state in question, it would not be appropriate to wait for a negative COVID test in our judgement.

Attachments

Data Collection: List the data or attach a list of the data to be collected about or from each subject (e.g. interview script, survey tool, data collection form for existing data).

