[To view what materials are currently attached to your application, go to "Application Links" in the menu bar on the left and click "All Attachments".]

Attachments

Attach Type	File Name
AddInfoConsiderations	57411 [name].pdf

Statistical Analysis

Continuous data will be described using medians and interquartile ranges. Discrete data will be described as counts and percentages. Changes in biomarker measurements will be calculated by subtracting the biomarker measurement at subsequent timepoint from the baseline biomarker measurement at enrollment. Assuming non-normal distributions of biomarker measurements with extreme elevations as well as skewness of the data for lengths of stay, continuous variables will be compared using the Mann-Whitney U test while discrete data will be compared between groups using chi-squared or Fisher's exact test as appropriate. A p-value <0.05 will be considered statistically significant.

Interim Analysis

Following enrollment of the 10 patients in the control arm and 10 patients in the angiotensin II arm (i.e. half of the 20 patients that will ultimately receive the drug), we will evaluate the risk of venous thromboembolism and any additional reported thrombotic reports from the 10 patients that have received angiotensin II. Groups will be compared using a Fisher's exact test given the small sample size. Given the concern for safety, if the p-value is 0.15 or less with increased thrombotic events in the angiotensin II group, the open-label study will be stopped. For example, assuming a baseline rate of thrombotic events of 1/10 (10%) in the control arm, if 5/10 patients in the angiotensin II group (50%) experienced a thrombotic event, a Fisher exact test yields $p=0.141$ and the open-label use of angiotensin II would be stopped due to concern for safety. If thrombotic event differences do not meet this threshold, we will continue with the enrollment of an additional 10 patients to meet the 20 patient enrollment set.

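### The off-vasopressor biomarker sample is, by inference, tested between arms although it comes only from weaned patients at unequal times; secondarily, length of stay has no rule for death

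*Combined protocol and SAP*

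**What the plan says.** All references are to the combined protocol and SAP.

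- **Statistical Analysis.** "Changes in biomarker measurements will be calculated by subtracting the biomarker measurement at subsequent timepoint from the baseline biomarker measurement at enrollment". With skewed biomarkers assumed, and likewise "skewness of the data for lengths of stay, continuous variables will be compared using the Mann-Whitney U test", at p<0.05. No time point is named or excepted. Nothing covers missing samples, elapsed time or death.
- **Research Procedures, control group.** Blood is drawn "once the patient meets inclusion criteria (time T), 24 hours later (time T + 24 hours"), and again after at least 4 h off vasopressors. "If the patient ceases vasopressor agents within 12 hours of the second blood draw, the third and final blood draw will not be collected".
- **Research Procedures, intervention group.** Blood is drawn at eligibility, 3 h later, "and 24 hours from angiotensin II initiation (T+24 hours"), and again after at least 4 h off vasopressors. "If the patient ceases vasopressor agents within 12 hours of the third blood draw, the fourth and final blood draw will not be collected".
- **Objectives.** Objective 1 is "To determine if prescription of angiotensin II is associated with faster declines in plasma renin compared to a control group". Objective 2 asks about improvement of functional renal biomarkers.
- **Benefit vs. Risk.** One hypothesised benefit of the drug is "fewer vasopressors required to maintain their blood pressure".
- **Data Collection.** In-hospital mortality and ICU and hospital length of stay are listed as outcomes, with no rule joining them.
- **Study Design.** Ten controls are enrolled first, then 20 treated patients. Allocation is not randomised.

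**The concern.** The last sample is triggered by an event, not by the clock. A patient who dies on vasopressors never gives it, and some patients who come off quickly are skipped by rule. If the drug lowers vasopressor need, as the protocol hopes, it changes both who gives the sample and when. A between-arm test there conditions on a post-treatment outcome and compares changes accrued over different numbers of hours. A change over unequal times cannot show a faster decline. If a marker falls as shock resolves, a drug that shortens shock leaves it less time to fall, so a drug that works on shock could look worse on renin.

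Only two post-baseline samples are shared by both arms, because the 3 h draw exists only in the treated arm. The other shared sample, at 24 h, avoids the weaning condition, but its clock starts at different points in the two arms.

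Separately, if length of stay is ranked without regard to death, an early death counts as a short stay.

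**Working it through.** The plan gives no figure on this point. Its one computed figure, the interim Fisher example (5/10 vs 1/10), reproduces as two-sided p=0.1409 against the stated 0.141, and has no bearing here. The documents give no rates, so every input below is an assumption.

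**1. What elapsed time alone does.** Suppose the marker halves every 24 h in both arms, with no drug effect. The fraction of baseline remaining at draw time t is 2^(-t/24), where t = weaning time + 4 h. At the median, before any skipping:

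- Control, weaned at 48 h: t = 52 h, 2^(-52/24) = 0.22, decline 78%.
- Treated, 25% faster (36 h): t = 40 h, 2^(-40/24) = 0.31, decline 69%.
- Treated, 50% faster (24 h): t = 28 h, 2^(-28/24) = 0.45, decline 55%.

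The treated arm shows the smaller decline purely because it was sampled earlier.

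**2. What that does to the test.** Simulated trials of 10 vs 20 patients, two-sided Mann-Whitney. Weaning time is log-normal (log-SD 0.8, control median 48 h), and one third of each arm is not weaned. Change is taken on the log scale with residual SD 1.0; less residual noise raises the rates. The 12 h wording can be read three ways:

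| Stops skipped | Equal weaning | 25% faster | 50% faster |
|---|---|---|---|
| 24-36 h | about 4% | about 8% | about 20% |
| 12-36 h | about 4% | about 5% | about 13% |
| any by 36 h | about 4% | not raised | not raised |

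The excess rejections are mostly against the drug. A separate model mixed timing with selection: control median weaning about 3 days, about 40% dying before weaning, and any stop by 36 h skipped. It gave 3.6-4.9% at equal weaning and 5.6%, 8.6% and 10.3% when treated patients weaned 0.5, 1.0 and 1.5 days earlier. The size therefore depends on the weaning times as well as on the reading of the rule.

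**3. What selection alone does.** Here severity drives weaning time, death before weaning and biomarker change, but change does not depend on elapsed time. With 33% dying before weaning in both arms and weaning 25-50% faster on drug, the shift in mean change (plus = towards the drug) is 0 to +0.10 SD if stops at 24-36 h are skipped, -0.04 to +0.31 SD for 12-36 h, and -0.30 to -0.04 SD for any stop by 36 h. The sign is not fixed. In three scenarios per reading, false positives did not exceed 5%.

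**4. Numbers.** With stops at 24-36 h skipped, about 5-6 of 10 controls and 11-13 of 20 treated patients give the sample. With 6 vs 11 samples, the difference detectable at 80% power is about 1.6 SD, against 1.2 SD with 10 vs 20.

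**5. The 24 h clock.** If the drug starts d hours after the baseline draw, the treated sample is taken at 24 + d hours. With no drug effect the treated value is lower by 1 - 2^(-d/h), where h is the half-life. For d = 4 h this is 1 - 2^(-4/24) = 10.9% at h = 24 h, and 6% to 21% for h = 48 h to 12 h. For d from 1 to 6 h it is 1% to 29%. The documents do not give d.

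Dividing raw change by hours does not repair this. At d = 4 h and h = 24 h, raw change is 1 - 2^(-28/24) = 0.555 against 0.500, an excess of 10.9%. Per hour it is 0.555/28 = 0.0198 against 0.500/24 = 0.0208, a deficit of 4.9%. At h = 12 h, +6.9% becomes -8.4%, which is larger. The log ratio to baseline divided by hours equals -ln 2/h in both arms, with no bias under this model.

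**6. Length of stay.** Stays are log-normal (log-SD 0.7), with median 12 days in survivors and 4 days in decedents. At 50% vs 30% mortality, the arm with fewer deaths ranks as longer-stay in 73-74% of trials and significantly so in about 8%, against 2% at equal mortality. At 40% vs 35% the figures are 56% and 3%. If decedents stay as long as survivors, they are 50-51% and 2%. With deaths ranked worst (50% vs 30%), the arm with fewer deaths is favoured in 81-82%, significantly in 13-14%.

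**The case against.** The plan never names the last draw as a tested endpoint. That it is tested follows from general wording, and the attached proposal might say otherwise. This stands, and the point is made as an inference. Objective 2 asks about improvement, not speed, so a value at shock resolution is a reasonable descriptive milestone; the elapsed-time objection bears chiefly on objective 1. The inflation rests on assumed weaning rates and on the reading of the 12 h rule. That also stands.

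A reader might infer more than the documents support:

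- **That selection biases the result in a known direction, or inflates false positives by itself.** It does neither in step 3.
- **That the sample would nearly vanish.** Very small counts come mainly from reading the rule as skipping any stop by 36 h, which is furthest from its words: a patient who stopped at hour 5 did not stop within 12 h of a 24 h draw.
- **That every biomarker comparison fails.** The 24 h sample does not depend on weaning. Its clock error depends on the interval from baseline draw to drug start. Research blood requires consent, so that interval may be shorter than eligibility to drug start.
- **That the length-of-stay result will reverse.** That needs both a mortality difference and shorter stays in decedents, and stay is not an objective.

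Carrying the 24 h value forward to patients who miss the last draw has a timing cost, but nothing here rules it out.

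**Conclusion.** The concern holds in this form. Applied as written, the analysis section compares the off-vasopressor change between patients selected on a post-treatment outcome and sampled at unequal times. Such a comparison cannot show a faster decline.

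Timing is the main problem. Under the inputs in step 2 with stops at 24-36 h skipped, a drug with no biomarker effect that speeds weaning by 25-50% gives about 8-20% rejection instead of about 4%, mostly against the drug. This falls to about 5-13% if stops at 12-36 h are skipped, and is not seen on those inputs if any stop by 36 h is skipped. The mechanism follows from the protocol's text; the size does not, since no rates are given.

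The 24 h sample is the better contrast, though its clocks need attention. Length of stay is secondary and matters only if mortality differs and decedents stay for less time. In a 30-patient sequential, non-randomised study, case-mix differences may outweigh all of this. The plan should be changed, but the point does not undermine the study.

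**What to change.** 1. Make the 24 h change the tested between-arm biomarker contrast. Record and report by arm the actual hours from baseline draw to that sample, and the deaths before it. Reconcile the two starting points of the 24 h clock in Research Procedures. If a time-scaled sensitivity analysis is wanted, use the log ratio to baseline divided by hours, not raw change divided by hours.
2. Report the off-vasopressor sample descriptively, with hours from baseline and with numbers and reasons for missing samples by arm (death before weaning, 12 h rule, other). Reconcile how the 12 h wording is to be read in both arms.
3. Do not test length of stay with deaths counted at their actual stay. Report survivors-only stay beside in-hospital mortality. A Mann-Whitney test with deaths ranked worst is one option, labelled as a stay-survival composite.

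The cost is SAP wording plus recording actual draw times, which the Data Collection list does not name. Deaths, stays and vasopressor dosing are already collected. The downside is that the last sample loses its significance test.
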